#### 5.6. 2-week follow-up after implant placement

- a. Evaluate wound closure, epithelialization, and any complications
- b. Take standardized CBCT, limited to the implant site\*
- c. Perform localized prophylaxis
- d. Take intraoral photos

#### 6.7. 6-week follow-up after implant placement

- a. Evaluate wound closure, epithelialization, and any complications
- b. Perform localized prophylaxis
- c. Take intraoral photos

#### 7.8. 3-4-month follow-up after implant placement

- a. Evaluate wound closure, epithelialization, and any complications
- b. Evaluate pocket depth, plaque index, bleeding index, and gingival index
- c. Measure ISQ by using Osstell Beacon (Osstell®, Gothenburg, Sweden)
- d. Take standardized ~~periapical and~~ bitewing and non-standardized periapical

- radiographs
- e. Perform localized prophylaxis
- f. Take intraoral photos
- g. Uncover the implant, if needed (and 2-week follow-up after uncovering)
- ~~8.9.~~ Restoration by the restorative dentist
- ~~9.10.~~ 2-week follow-up after implant restoration
  - a. Evaluate pocket depth, plaque index, bleeding index, and gingival index
  - b. Evaluate biological (i.e. peri-implant mucositis, peri-implantitis) and restorative complications (i.e. screw loosening, porcelain fracture)
  - c. Take standardized ~~periapical and~~ bitewing and non-standardized periapical radiographs
  - d. Perform localized prophylaxis
  - e. Take intraoral photos
- ~~10.11.~~ 1-year Follow-up after implant restoration
  - a. Evaluate pocket depth, plaque index, bleeding index, and gingival index
  - b. Evaluate biological (i.e. peri-implant mucositis, peri-implantitis) and restorative complications (i.e. screw loosening, porcelain fracture)
  - c. Take standardized bitewing and non-standardized periapical radiographs
  - ~~e. Take standardized periapical and bitewing radiographs~~
  - d. Take standardized CBCT, limited to the implant site\*
  - e. Perform localized prophylaxis
  - f. Take intraoral photos
- ~~11.12.~~ Data analysis
  - a. Evaluation of change in peri-implant bone density, using the ImageJ software (National Institute of Health, Bethesda, Maryland, USA)\*
  - b. Statistical analysis of changes in the parameters throughout the study period\*

#### 4. Inclusion / Exclusion Criteria

The inclusion criteria include:

1. Adult patients  $\geq 18$  years old
2. Able to understand and sign a written informed consent form and willing to fulfil all study requirements
3. Healed edentulous ridge that is planned for an implant restoration.
4. Experimental site has not been previously augmented with xenograft
5. Experimental site has at least 2 mm of cancellous bone

The exclusion criteria include:

1. Uncontrolled systemic disease
2. Currently smoking  $>10$  cigarettes/day
3. History of head/neck radiotherapy within the past five years
4. Current use of oral bisphosphonates or history of IV bisphosphonate use
5. Pregnant, expecting to become pregnant, or lactating women
6. Presence of active periodontal disease
7. Poor oral hygiene
8. Previous history of implant failure at the site

[figure not shown]
The early termination criteria include:

1. The researcher believes that it is not in the patient's best interest to stay in the study

2. Based on the exclusion criteria, the patient becomes ineligible to participate
3. Patient's medical condition requires interventions which preclude involvement in the study (radiation therapy, chemotherapy, etc)
4. Patient does not follow study related instructions
5. The study is suspended or canceled

If subjects do not qualify or decide not to be part of this study, same treatments can be performed but without being part of this study. If subjects decide not to receive the treatments, consequences and probable outcomes will be explained.

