In a studyError! Bookmark not defined. on porcine oral alveolar bone, 80% ridge expansion was recorded immediately after osseodensification. After 4 weeks of healing, the animals were euthanized and samples were processed for histological evaluation. This was the first study to evaluate the amount of ridge expansion in atrophic mandibular ridge. Apart from being an animal model with a short follow-up, another limitation of this study is the method of recording the expansion. Transverse dimension of the ridge was measured with a periodontal probe, immediately before and after osseodensification. Measurements were only at one dimension, without three-dimensional evaluation of the change in morphology of the ridge. Also, there is no record if this bone volume is retained during osseointegration and loading.

A few human case reportsvii,viii,ix and case seriesx,xi have reported significant ridge expansion immediately before and after osseodensification. They evaluated the expansion by measuring the ridge width at a crestal and an apical point, which again lacks an evaluation of ridge morphology in a three-dimensional view. Using the same methodology, a recent retrospective studyxi on 28 implants found a mean expansion of  $1.8 \pm 1.1$  mm at the crest and  $0.9 \pm 0.8$  mm at 10 mm mark apical to the crest, immediately after expansion. They reported greater expansion at narrow ridges. None of the mentioned studies report on retention of this volume over time, nor was standardization methods or evaluation of peri-implant health reported.

Although promising improvements in bone density and volume have been reported, there is a lack of clinical trial in humans with adequate follow-up period. Our research is motivated by this gap and our objective is to further investigate this phenomenon. We propose a human case series to evaluate the amount of ridge expansion and the survival and success rates of implants placed by using the osseodensification technique.

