## 8. Statistical Methods

The biostatistics department at OUHSC will be utilized to review the data and perform statistical evaluation. Mean values, standard deviations, and medians will be calculated for clinical measurements. We will compare the bone volumetric changes before ridge expansion to different time points throughout healing. In addition, we will determine the implant survival and success rates by evaluating the probing pocket depth, bleeding index, gingival index, interproximal crestal bone level changes, biological and restorative complications of implants placed by the osseodensification technique. A fixed-effects regression model can account for correlations between repeated measures taken at each implant over time. This model can estimate a regression equation that describes the within-group changes.

Approximately 40 implants from patients seeking treatment at the University of Oklahoma, College of Dentistry will be recruited for this study. It is estimated that this sample size will provide 90% power of the test.

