## 9. Data and Safety Monitoring Plan

The investigators will periodically audit the study records of each participant to evaluate the progress of the study, verify its accuracy and completeness, and resolve any inconsistencies in the study records. The Principal Investigator may stop the study if it is observed that the protocol or sound clinical practices are not being followed. The Principal Investigator may exclude subjects from the study if review of their records indicates violations of the protocol or if there are other reasons to believe that their inclusion would jeopardize the validity of the study. Subjects discontinued due to adverse events will not be replaced.

The investigator will make an accurate and adequate written progress reports to the IRB at appropriate intervals, not exceeding one year, and a final report to the IRB within 3 months after completion or termination of the study. The investigator will make an accurate and adequate special report to the IRB on any serious, unexpected, or life-threatening adverse

event or death occurring in relationship to the study whether regarded as study-related or not.

Any adverse event, including both observed or volunteered problems, complaints, or symptoms, are to be recorded as mild, moderate or severe as follows:

- MILD: events are usual transient, requiring no special treatment, and do not interfere with the subject's daily activities.
- MODERATE: events traditionally introduce a low level of inconvenience of concern to the subject and may interfere with daily activities, but are usually ameliorated by simple therapeutic measures.
- SEVERE: events interrupt a subject's usual daily activity and traditionally require systemic drug therapy or other treatment.

When intensity changes occur more frequently than once a day, the maximum intensity for the event should be listed. If the intensity category changes over a number of days, then these changes should be recorded separately (i.e. having distinct onset days).

The investigator will determine the relationship of the adverse event to the study test material. One of the following determinations will then be used to document the relationship of the adverse event to the study test material:

- NOT RELATED
- POSSIBLE
- PROBABLE

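### Removal rules overlap with the trial's outcomes and no analysis set keeps removed patients, so survival and retention can be overstated and complications understated

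*Combined protocol and SAP*

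**What the plan says.** **Removal under Section 4.** Item 2 of the early termination criteria applies when "Based on the exclusion criteria, the patient becomes ineligible to participate". The verb describes a change after enrolment, so the exclusion list is consulted again during follow-up. Three items on that list matter here: item 6, "Presence of active periodontal disease"; item 7, "Poor oral hygiene"; and item 8, "Previous history of implant failure at the site". Items 6 and 7 have no threshold. Two other termination grounds are the researcher's view of the patient's interest and failure to follow instructions.

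**Removal under Section 9.** "The Principal Investigator may exclude subjects from the study if review of their records indicates violations of the protocol". The same sentence adds a second, open-ended ground: any other reason to think that keeping the subject would threaten the study's validity. Replacement is ruled out only after discontinuation for an adverse event; other removals are not addressed.

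**Outcomes.** Section 1 makes retention of bone volume through loading part of the primary aim. Its secondary outcomes include survival and failure, pocket depth, the plaque, bleeding and gingival indices, and peri-implant complications. Under Section 3 the indices and pocket depth are recorded at 3-4 months, 2 weeks after restoration and 1 year after restoration. The last CBCT is at 1 year.

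**Analysis.** Section 8 says: "Approximately 40 implants from patients seeking treatment at the University of Oklahoma, College of Dentistry will be recruited for this study". It promises summary statistics, survival and success rates, and a regression for repeated measures. It names no analysis set, survival denominator, missing-data rule or follow-up after termination. No section says whether a removed patient's data are kept or dropped.

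**The concern.** Some grounds for removal are the outcomes themselves or lie close to them. A worsening plaque score is a secondary outcome and could also be the evidence that a patient now has poor hygiene. Active periodontal disease is related to bleeding, gingival inflammation and pocket depth. The Section 9 power is exercised after reading the records, and the documents describe no masking, so whoever decides can see how the implant is doing.

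There is no control arm, so the observed rates are the result. If patients who do badly are more likely to leave and their data leave with them, the rates describe those who did well. Two features could add to this. Termination acts on the patient while the sample is counted in implants, so where a patient has several study implants one trigger could remove them all. A patient removed for a reason other than an adverse event could also, as far as the text goes, be replaced.

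**Working it through.** **1. The plan's own figure.** The stated sample is about 40 implants, and "It is estimated that this sample size will provide 90% power of the test". The test, endpoint, alpha, effect size and SD are not given, so the figure cannot be reproduced. With an assumed two-sided alpha of 0.05 and a paired t test, 40 implants give 90% power for a standardised change of about 0.53 (one-sided, 0.47). The only effect sizes in the document are from the retrospective study of 28 implants in Section 2. Taking its SDs as SDs of change, they are 1.8/1.1 = 1.64 and 0.9/0.8 = 1.13, which would need only about 7 and 11 implants. They do not explain 40. Only the count of 40 is carried forward.

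**2. Expected failures.** Section 7 cites 92.8% survival (26/28 = 92.9%).
- Expected failures: 40 × (1 − 0.928) = 2.9, taken as 3.
- Chance of at least one failure, if implants are independent: 1 − 0.928^40 = 0.95.

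**3. Survival when r of the 3 failures leave the denominator.** Survival = 37/(40 − r), with exact (Clopper-Pearson) 95% intervals.

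| Failures removed | Survival | 95% CI | Shift (points) |
|---|---|---|---|
| 0 | 37/40 = 92.5% | 79.6 to 98.4% | 0 |
| 1 | 37/39 = 94.9% | 82.7 to 99.4% | +2.4 |
| 2 | 37/38 = 97.4% | 86.2 to 99.9% | +4.9 |
| 3 | 37/37 = 100% | 90.5 to 100% | +7.5 |

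With 2 or 4 failures the largest possible shift is 5.0 points (95.0% to 100%) or 10.0 points (90.0% to 100%). A failure that is recorded and counted before removal contributes no shift.

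**4. Complications.** If a true share c of implants is affected and a share q of those is removed, the observed rate is c(1 − q)/(1 − cq). The document gives no complication rate, so c is assumed. For q = 0.5:
- c = 10%: 0.05/0.95 = 5.3%
- c = 20%: 0.10/0.90 = 11.1%
- c = 30%: 0.15/0.85 = 17.6%

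For q = 1 the observed rate is 0%. The direction is downward.

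**5. Retention.** If affected sites retain d mm less, removal raises the mean by d × [c − c(1 − q)/(1 − cq)]. All inputs are assumed: c from 10% to 30%, d from 0.5 to 1.0 mm, q from 0.5 to 1.
- Smallest: 0.5 × (0.100 − 0.053) = 0.02 mm.
- Largest: 1.0 × 0.30 = 0.30 mm.

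**6. Precision.** Under the assumptions of step 1, losing 4 or 8 of 40 implants at random lowers 90% power to about 87% or 82%. Random loss causes no bias; the problem is loss related to outcome.

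**The case against.** The strongest reply is that the rules end participation and do not delete data. Bias needs two further steps that the plan does not state: applying the criteria to events after placement, and leaving out what was already recorded.

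A reader might infer that failure of the study implant is itself a termination criterion. The text does not support that. Item 8 most naturally refers to failure before the study, and a rule that erased every failure would defeat the aim of reporting survival and failure. The design also expects patients with complications to stay: Section 3 foresees extra visits for them, schedules prophylaxis at each post-surgical follow-up visit, and assesses peri-implant mucositis and peri-implantitis 2 weeks and 1 year after restoration. The exclusion list names periodontal disease, not those peri-implant conditions. Protocol violations are not an outcome either, and removal for them biases results only if it is related to prognosis.

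These points limit the claim but do not dispose of it. Items 6 and 7 overlap with recorded outcomes without any help from item 8. The Section 9 discretion is explicit and open-ended. Silence on whether data are kept gives no protection, because nothing requires a failure to be counted before a patient is removed.

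**Conclusion.** The point holds as a risk that the written rules permit. Applied as written, Sections 4 and 9 allow outcome-related removal from a single-arm study, and Section 8 does not keep the affected implants in the analysis. The favourable direction is upward for survival and 1-year retention and downward for complications.

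With 3 failures in 40, the survival bias lies between 0 and +7.5 points. A reader might take 100% as what the rule produces. It is the extreme case, in which every failure is removed and none is counted. It would also be too strong to say that the results are biased, since the documents do not say how removed patients' data will be handled. The retention shift of 0.02 to 0.30 mm and the complication figures rest wholly on assumed inputs; the retention shift is small unless affected sites are common and much worse than the rest. The survival illustration borrows the cited 92.8%, and its intervals treat implants as independent.

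**What to change.** - **Section 8:** define the analysis set as every implant placed, and count failures and complications up to and including the time of removal. Report all removals with reasons, and add a worst-case sensitivity analysis for survival in which removed implants of unknown status count as failures.
- **Section 9:** replace exclusion of subjects from the study with a statement that protocol violations are listed and used only in a sensitivity analysis.
- **Section 4:** clarify that exclusion items 6 to 8 determine eligibility at baseline and do not take an implant out of the analysis. Separate stopping research procedures from stopping outcome collection, so that implant status and complications from routine visits are still recorded where the patient agrees.

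Early-termination item 2 need not be deleted. It also covers exclusion criteria unrelated to the outcomes, and the analysis can be protected without changing when a patient leaves. Decisions to stop research procedures for clinical reasons stay with the investigators.

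The cost is a few sentences of protocol text, best settled before the data are analysed, and some recording from routine visits. Reported survival and success may be slightly lower.

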## 5. **Gender/Minority/Pediatric Inclusion for Research**

There will no exclusion on the bases of race or gender. A translator will be provided to those that do not speak English, including Spanish speaking subjects. Patients under 18 years old will be excluded. Placement of implant is not indicated in children due to ongoing growth potential of alveolar bone at younger age.

## 6. **Recruitment and Enrollment**

This investigation will be conducted at the University of Oklahoma, College of Dentistry, Department of Graduate Periodontics. Potential participants will be selected from the new and established patients of the College of Dentistry and will be contacted by the study coordinator by telephone for information regarding the participation in the study. Subjects that may qualify based on the inclusion and exclusion criteria will be scheduled for a screening examination appointment. Patient and the intervention site will be further evaluated at the screening appointment to confirm that patient qualifies to participate in the study.

Study personnel will provide each study candidate with a written informed consent form at the screening appointment at Graduate Periodontics clinic, prior to administration of any research related procedures. The protocol, procedures and objectives of the study and the patient's role in the study will be explained to each subject and/or legal guardian/authorized representative, before obtaining consent. Subjects will be given the opportunity to read the informed consent. Study personnel will answer all questions that the subject may have and ensure that the subject understood all aspects of the study. When the subject (or legal guardian/authorized representative) understands and is willing to (have the subject) participate in the clinical trial, he/she (or the legal guardian/authorized representative) must sign and date the Institutional Review Board (IRB) approved Informed Consent Form.

A translator will be provided for the participants that do not speak English. A witness that can speak both English and the patient's language will be present and will sign the Consent Form.

## 7. **Risks and Benefits**

In preparation of the dental implant osteotomy, the osseodensification technique uses non-subtracting drills to compress the trabecular bone to periphery of the osteotomy site rather than removing it. As a result, there will be more bone available at the site for primary stability of the implant. This technique also expands the alveolar ridge and allows for placement of wider implants without the additional need for bone augmentation. By avoiding bone augmentation, this technique will not only be more cost effective, but also reduces treatment time and morbidity.

Animal studies and human case reports have reported significant ridge expansion, but there is a lack of randomized controlled clinical trial in humans. Because of this gap in knowledge, we do not know if the implants prepared with osseodensification technique, using the Densah® burs by Versah®, will be successful in the long term and if the expanded bone is retained or resorbed. A retrospective studyxi observed 92.8% survival rate of the implants and high implant stability quotient value 6 weeks after placement. Details about marginal bone loss or status of peri-implant health or inflammation were not reported. Based on the

available data, the risk of implant failure is low when using the Densah® burs by Versah® to create the osteotomy and the risk of adverse events is similar to conventional techniques. We would like to further investigate if peri-implant health is maintained in long-term.

As with any surgery, there are risks involved, some common risks include, but are not limited to:

- Swelling and/or bruising and discomfort in the surgical area.
- Possible damage to adjacent teeth.
- Possible damage to nerves which causes numbness or altered feeling in the teeth. In rare cases the numbness is permanent.

Complications that do occur are often minor and can be treated. Every possible effort will be made to minimize the risks involved.

For volumetric assessment of the peri-implant bone, we propose to take a series of CBCT. The radiographs will be limited to the area of the implants to reduce the radiation exposure. Lead apron with thyroid collar will be used to limit radiation exposure to radiosensitive organs.

## 8. Statistical Methods

The biostatistics department at OUHSC will be utilized to review the data and perform statistical evaluation. Mean values, standard deviations, and medians will be calculated for clinical measurements. We will compare the bone volumetric changes before ridge expansion to different time points throughout healing. In addition, we will determine the implant survival and success rates by evaluating the probing pocket depth, bleeding index, gingival index, interproximal crestal bone level changes, biological and restorative complications of implants placed by the osseodensification technique. A fixed-effects regression model can account for correlations between repeated measures taken at each implant over time. This model can estimate a regression equation that describes the within-group changes.

Approximately 40 implants from patients seeking treatment at the University of Oklahoma, College of Dentistry will be recruited for this study. It is estimated that this sample size will provide 90% power of the test.

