## 1. **Specific Aims**

Primary Aim:

Evaluate the efficacy of osseodensification technique in regards to increase in alveolar bone volume and density at time of implant placement and retention of this volume throughout osseointegration and loading.

Secondary Aim:

Evaluate the osseodensification technique for preparation of implant osteotomy, in regards to implant stability, survival and failure rate, probing pocket depth, plaque index, bleeding index, gingival index, interproximal crestal bone level changes, biological complications (i.e. peri-implant mucositis, peri-implantitis), and restorative complications (i.e. screw loosening, porcelain fracture). These outcomes will be evaluated from the time of implant placement until 1 year after final restoration is delivered.

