### 3. **Research Design and Methods**

This case series will assess the efficacy for alveolar ridge expansion and change in peri-implant density when prepared by the osseodensification technique. The retention of this volume throughout osseointegration and loading will be evaluated. The changes in bone volume will be recorded by CBCT and intra-surgical direct measurements. A standardizing stent will be used to for direct measurements with a caliper. Radiopaque markers on this stent will guide the measurements on the CBCT. CBCT will be taken before and after osseodensification, and 1 year after delivery of final restoration. Standardized ~~periapical and~~ **bitewing** radiographs will be taken as well to evaluate marginal bone loss and peri-implant bone density. Calibrated examiners will evaluate implant survival and failure rate, ISQ value,

peri-implant pocket depth, plaque index, bleeding index, gingival index, biological and restorative complications.

All the surgical interventions and follow-up appointments will be conducted at the University of Oklahoma, Graduate Periodontics clinic. Restorative interventions will be scheduled with the restorative dentist of the patient's choosing. Approximately 10 visits are anticipated for each patient. Additional appointments may be needed depending on surgical or restorative complications that need attention or intervention. Following the completion of the study, the participants are placed on appropriate recall schedule either at the Graduate Periodontics clinic or referred to their dentist of choosing.

Informed consent will be obtained from the patients. Appropriate steps will be taken to protect collected data and de-identify it before data analysis. Identifiers will be removed and the de-identified information may be used for future research without additional informed consent from the subjects. Patient information will be protected according to the privacy regulations of the federal Health Insurance Portability and Accountability Act of 1996 (HIPAA).

*\* Research specific procedure*

Planned Visits:

1. Pre-screening
  - a. Preliminary review of eligibility criteria\*
2. Screening
  - a. Confirm eligibility\*
  - a.b. Informed consent\*
  - c. Diagnostic casts
3. Fabrication of measurement stents
  - a. Fabrication of custom stent for measurement of alveolar ridge width\*

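### Section 8 relies on a fixed-effects model for repeated measures without a covariance structure or standard-error method; in its default form every visit contrast gets the same standard error, which can be wrong in either direction

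*Combined protocol and SAP*

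**What the plan says.** Section 8 (Statistical Methods) plans means, standard deviations and medians, and then a comparison over time: "We will compare the bone volumetric changes before ridge expansion to different time points throughout healing". The method offered for repeated measures is "A fixed-effects regression model can account for correlations between repeated measures taken at each implant over time", followed by "This model can estimate a regression equation that describes the within-group changes". The section does not state a covariance structure, a standard-error method, how time is coded, or which contrasts will be tested.

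The primary aim in Section 1 has two parts: "increase in alveolar bone volume and density at time of implant placement and retention of this volume throughout osseointegration and loading". Section 3 sets three CBCT time points: "CBCT will be taken before and after osseodensification, and 1 year after delivery of final restoration". The visit list places the second of these at the 2-week follow-up. It also schedules six standardized bitewings: before surgery, after the osteotomy, after implant placement, at 3-4 months, 2 weeks after restoration and 1 year after restoration. Section 8 gives the size as about 40 implants, with no number of patients.

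**The concern.** An ordinary fixed-effects regression with one effect per implant removes each implant's own level. It then judges every visit contrast against one pooled residual variance. Removing the level deals with correlation only if the change between any two visits has the same variance.

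This design gives reason to doubt that. The step from before to after surgery contains an expansion that varied considerably in the background study cited in Section 2. The step from after surgery to 1 year contains healing and loading, with no second expansion. The intervals between measurements run from minutes within the operation to more than a year.

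At stake are the two contrasts that carry the primary aim: net change from pre-expansion to 1 year, and change from post-expansion to 1 year, which is the direct measure of retention. If the common standard error is too small for a contrast, its test rejects too often; if it is too large, a real change can be missed. The issue arises even with one implant per patient, so it is separate from several implants sharing a patient.

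**Working it through.** **The plan's own figure.** Section 8 claims 90% power without an alpha, effect size, SD or named test, so it cannot be reproduced. A two-sided 5% paired t-test with n = 40 has 90% power at a standardized change of 0.53. The background effects are far larger (1.8/1.1 = 1.64 and 0.9/0.8 = 1.125) and would give over 99.9%. The power statement therefore does not show which test was intended.

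**Inputs.** From the documents: n = 40, three CBCT visits and an expansion SD of s1 = 1.1 mm (Section 2, retrospective study of 28 implants). Assumed: the late-change SD s2, its correlation r with expansion, independent implants, and a two-sided 5% level.

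**Formulas.**
- True variance of expansion: s1² = 1.21.
- True variance of late change: s2².
- True variance of pre-expansion to 1 year: V = s1² + s2² + 2·r·s1·s2.
- Variance used by the common-variance model for every contrast: M = (s1² + s2² + V)/3.
- Model SE divided by true SE: √(M/V) for pre-expansion to 1 year, and √(M/s2²) for late change.
- Rejection rate under no mean change: 2·(1 − Φ(1.96 × ratio)).
- Power for a late loss that the paired test detects at 90%: about Φ(0.526·√40 − 1.96 × ratio).

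**Worked case, s2 = 0.6, r = 0.** V = 1.21 + 0.36 = 1.57 and M = (1.21 + 0.36 + 1.57)/3 = 1.047. The ratios are √(1.047/1.57) = 0.816 and √(1.047/0.36) = 1.705. Rejection for pre-expansion to 1 year is 2·(1 − Φ(1.60)) = 11.0%. Late power is Φ(3.32 − 3.34) = 49%, or 48% by simulation. With r = 0, V/M is always 1.5, so the 11% does not depend on s2.

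| Late SD (mm) | r | SE ratio, pre to 1 year | SE ratio, late change | Rejection, pre to 1 year (nominal 5%) | Late power (paired 90%), simulated |
|---|---|---|---|---|---|
| 0.6 | 0 | 0.82 | 1.71 | 11.0% | 48% |
| 0.6 | -0.3 | 0.88 | 1.59 | 8.4% | 56% |
| 0.6 | -0.5 | 0.95 | 1.52 | 6.2% | 62% |
| 0.8 | 0 | 0.82 | 1.39 | 11.0% | 71% |
| 0.8 | -0.5 | 0.98 | 1.21 | 5.4% | 82% |
| 0.8 | -0.6 | 1.05 | 1.17 | 3.9% | 84% |
| 1.1 | 0 | 0.82 | 1.15 | 11.0% | 85% |
| 1.1 | -0.5 | 1.00 | 1.00 | 5.0% | no loss |
| 1.5 | -0.6 | 1.05 | 0.86 | 3.9% | no loss, but the late test rejects about 9% under no change |

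Simulation with 20,000 runs per case agrees with the formula (11.5% against 11.0% at late SD 0.5 mm, r = 0). In seven simulated scenarios, paired standard errors held 4.6 to 5.3% for both contrasts. The common-variance model gave 3.9 to 11.5% for pre-expansion to 1 year and 0.0 to 4.9% for late change.

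**Six bitewings (density).** Suppose the five steps are equal and independent. The first-to-last variance is 5 units and the mean over all pairs is 35/15 = 2.33. The ratio is 5/2.33 = 2.14, and rejection is 2·(1 − Φ(1.96/√2.14)) = 18%. If reading error has the same SD as a step, the ratio is (5 + 2)/(2.33 + 2) = 1.62 and rejection is 12%. At reading SDs of two and three times the step SD, it is 8% and 6.5%.

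**The case against.** The strongest reply is that the text never says one residual variance will be used. It says that a fixed-effects model can account for the correlation, and it leaves the analysis to the biostatistics department. A fixed-effects model with robust standard errors would fit that sentence. This stands: the plan is under-specified, and the documents do not show that a wrong analysis has been chosen.

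A reader might also infer that the interval for pre-expansion to 1 year will be too narrow and the one for late change too wide. The documents do not support that as a fact. The direction depends on a late SD and a correlation that they do not give, and Section 2 says no cited study reports retention. The table has cases with no error, with both intervals too wide, and with the direction reversed.

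The 11% is also an unfavourable case. The post-expansion reading enters both steps with opposite sign, so reading error alone makes the observed correlation negative. Hold the observed expansion SD at 1.1 mm. With reading SD 0.6 and true late SD 0.3, the three variances are 1.21, 0.09 + 0.72 = 0.81, and 0.49 + 0.09 + 0.72 = 1.30. Their mean is 1.107, the ratio is 1.17 and rejection is about 7%. With reading SD 0.4 and true late SD 0.8, it is about 9.5%. If stable reading error dominates, the problem disappears.

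Three further limits stand. The 18% for density assumes equal steps, although two of the six films are taken within one operation. The 1.1 mm is immediate crestal expansion, whereas this study measures 2 and 4 mm apical to the ridge and takes its second CBCT at 2 weeks. Section 8 names comparisons with pre-expansion only; the late contrast follows from the retention aim.

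None of this makes the default model safe. With expansion SD 1.1 mm, its single standard error is right for all three CBCT contrasts only at late SD 1.1 mm and correlation -0.5, and nothing in the documents points there.

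**Conclusion.** The concern holds as a gap in specification with real consequences under the default form of the named model. Implant effects alone do not account for repeated-measures correlation when pairwise changes have unequal variances, and this design makes unequal variances likely.

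Under the stated assumptions, the nominal 5% test of pre-expansion against 1 year runs at about 11% with independent late change. It runs at about 5 to 9% at correlations of -0.3 to -0.5, and can fall below 5% at stronger negative correlation (3.9% at late SD 0.8 mm and -0.6). Power for a late loss falls from 90% to about 48-62% at late SD 0.6 mm, with no loss at 1.1 mm and -0.5. At 1.5 mm and -0.6, the late test is the one that rejects too often.

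These figures show how far the result can move; they do not predict this study's error. The conclusion that contrast-specific standard errors should be pre-specified does not depend on the direction.

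**What to change.** In Section 8, state that visit is a categorical factor and that each contrast uses its own variance: pre-expansion to each later visit, and post-expansion to 1 year.

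- **CBCT, three visits:** paired differences with 95% confidence intervals or, equivalently with complete data, an unstructured within-implant covariance.
- **Density, six films:** paired contrasts, or cluster-robust standard errors with a small-sample correction.
- **Clustering:** by patient wherever a patient has more than one implant.

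The fixed-effects model may stay if such standard errors are used. Drop only the claim that it accounts for the correlation by itself.

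The cost is wording, with no new data. An unstructured covariance has 6 parameters for three CBCT visits. It would have 21 for six films, which is many for about 40 implants and is why the simpler options are suggested there. In some scenarios the pre-expansion to 1-year interval becomes wider; in those, the common-variance interval was too narrow.
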